## 6.9 Data Safety Monitoring Board (DSMB)

Not relevant for this study.

## 6.10 Dissemination update safety information

Safety updates need to be reported yearly in the updated Investigator Brochure and/or annual safety report and in case of substantial safety changes these need to be reflected in an updated informed consent form and approved by the EC, prior to providing to the Trial participants.

## 7 Statistics and Data Analysis

Statistical analysis will be performed in accordance with ICH E9; a detailed description of the analysis is provided in the Trial-specific Statistical Analysis Plan (SAP). ICH E3 and E8 will guide the structure and content of the clinical trial report.

Twelve healthy volunteers will be enrolled in this placebo-controlled cross-over study. The number of volunteers to be included is calculated with a two-tailed t-test comparing two dependent means. We specified the following parameters: an error probability of 5%, effect size of 1.0 and a power of 80%. Based on these parameters we need to include 10 volunteers in order to highlight the expected differences. Twelve volunteers will be included to anticipate a potential dropout. Data from all subjects who completed the study will be included for analysis. Statistical analysis of the different parameters will be performed in SPSS for Windows (SPSS Inc., Chicago, IL, USA). Curves of whole blood glucose, plasma levels of motilin and ghrelin GLP-1, GLP-2, GIP and insulin and hunger / appetite scores over time will be

analyzed using the mixed models procedure, taking into account the course of the curves over different time points. Gastric motility and BA composition will be compared with Two-tailed paired t tests or Wilcoxon signed-rank tests, depending on data distribution. Non-parametric test were applied to analyse microbiome data, with multiple testing correction whenever applicable (adjustment for false discovery rate (FDR)).

## 7.1 Sample Size Determination

Twelve healthy volunteers will be enrolled in this placebo-controlled cross-over study. The number of volunteers to be included is calculated with a two-tailed t-test comparing two dependent means. Power calculations were based on previous results on the effect of cholestyramine (a bile acid sequestrant) on hunger sensation in healthy volunteers (23). We assume a similar effect of obeticholic acid on hunger sensation and a similar within-participant variability. We specified the following parameters: an error probability of 5%, effect size of 1.0 and a power of 80%. Based on these parameters we need to include 10 volunteers in order to highlight the expected differences. Twelve volunteers will be included to anticipate a potential dropout. Power calculations were performed with GPower version 3.0.10.

Approximately 15 participants will be screened to achieve 6 randomly assigned to Trial treatment and 6 evaluable participants for an estimated total of 12 evaluable participants per treatment group.

A maximum of 12 participants will be randomly assigned to Trial treatment such that approximately 10 evaluable participants complete the Trial.

## 7.2 Statistical Analysis

Data from all subjects who completed the study will be included for analysis. Statistical analysis of the different parameters will be performed in SPSS for Windows (SPSS Inc., Chicago, IL, USA). Curves of whole blood glucose, plasma levels of motilin and ghrelin GLP-1, GLP-2, GIP and insulin and hunger / appetite scores over time will be analyzed using the mixed models procedure, taking into account the course of the curves over different time points. Gastric motility and BA composition will be compared with Two-tailed paired t tests or Wilcoxon signed-rank tests, depending on data distribution. Non-parametric test were applied to analyse microbiome data, with multiple testing correction whenever applicable (adjustment for false discovery rate (FDR)). Data obtained from endoscopy and gastric motility measurements prior to the start of treatment in the first part of the crossover study will be used as pre-treatment data in the second part. Results will be found significant at  $p<0.05$  significance level.

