## 4 Trial Procedures

### 4.1 Participant consent and withdrawal of consent

The Trial will be conducted only on the basis of prior informed consent by the Trial participants and/or their legally authorized representative(s). As such, no Trial-related procedures will be conducted prior to obtaining written informed consent from potential Trial participants.

The process for obtaining and documenting initial and continued informed consent from potential Trial participants will be conducted in accordance with ICH-GCP E6(R2), applicable regulatory requirements and internal Standard Operating Procedures (SOPs).

All originally signed obtained Informed Consent Forms (ICFs) must be retained/archived in the Investigator Site File (ISF) at the Participating Site and must not be destroyed (even when a scanned copy is available) before expiration of the legal archiving term as defined in the protocol section entitled "Archiving".

Participants may voluntarily withdraw consent to participate in the Trial for any reason at any time. The participant's request to withdraw from the Trial must always be respected without prejudice or consequence to further treatment. Consent withdrawal will be documented in the participant's medical record.

Trial data and samples collected before withdrawal can be used in the trial. No new trial data or samples will be collected after withdrawal of the participant.

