#### **4.5 Premature discontinuation of Trial treatment**

Participants may voluntarily discontinue from Trial treatment and/or prematurely end their participation in the Trial for any reason at any time. In such case the Investigator must make a reasonable effort to contact the participant (e.g. via telephone, e-mail, letter) in order to document the primary reason for this decision.

The Investigator may also decide at any time during the course of the Trial, to temporarily interrupt or permanently discontinue the Trial treatment if it is deemed that continuation would be detrimental to, or not in the best interest of the participant.

Similarly, de Sponsor, Ethics Committee or authorized regulatory authority can decide to halt or prematurely terminate the Trial when new information becomes available whereby the rights, safety and well-being of Trial participants can no longer be assured, when de integrity of the Trial has been compromised, or when the scientific value of the Trial becomes obsolete and/or unjustifiable.

Circumstances requiring premature treatment interruption or discontinuation of the Trial, include but are not limited to:

- Safety concerns related to IMP or unacceptable intolerance
- Trial participation while in violation of the inclusion and/or exclusion criteria
- Pregnancy
- Intention of becoming pregnant

In any such case of early Trial termination and/or treatment interruption/discontinuation, the Investigator will continue to closely monitor the participant's condition and ensure adequate medical care and follow-up. It is recommended that follow-up information will be collected as follows:

The Investigator will assess physical damage at the end of treatment and provide medical care and follow-up as necessary

For participants whose status is unclear because they fail to appear for Trial visits without stating an intention to discontinue or withdraw, the Investigator must make every effort to demonstrate "due diligence" by documenting in the source documents which steps have been taken to contact the participant to clarify their willingness and ability to continue their participation in the Trial (e.g. dates of telephone calls, registered letters, etc.).

[figure not shown]
A participant should not be considered lost to follow-up until due diligence has been completed.

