## 5.3 Concomitant / Prohibited Medication / Treatment

The following drugs must not be used 2 weeks before, during and 1 week after the study

- Drugs that can affect gastrointestinal function, motility or sensitivity or gastric acidity.
- Centrally acting medication, including antidepressants, antipsychotics and/or benzodiazepines
- Warfarin
- Proton pump inhibitors

If these drugs are taken during study medication, IMP medication will be discontinued and the subject will be excluded from the study at that time. Study data up to the time of exclusion will be available.

If these drugs are taken during the washout period, a period of at least 2 weeks should be allowed before starting the second medication.

The following drugs must not be used 1 year before, during and 1 week after the study

- Centrally acting medication, including antidepressants, antipsychotics and/or benzodiazepines (in the last year before screening visit).

If these drugs are taken during study medication, IMP medication will be discontinued and the subject will be excluded from the study at that time. Study data up to the time of exclusion will be available.

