### 6.7.2 Timelines for reporting

After obtaining informed consent and prior to initiation of Trial treatment, only (serious) adverse events caused by a Trial specific procedure should be reported in the (e)CRF.

After initiation of Trial treatment, safety events will be reported as follows:

- All AEs, SAEs and AESIs occurring during Trial treatment or within 30 days after last Trial treatment administration, or last follow-up visit (whichever occurs first) will be reported.
- All SAEs and AESIs as defined in the protocol must be reported to the Sponsor within 24 hours of the Trial staff becoming aware of the event. The initial report shall be followed by detailed, written reports. Both the initial and follow-up reports shall identify participants only by their Trial-specific identification.
- SAE details will be reported by the Investigator to the Sponsor:
  - By completing the SAE form in the (e)CRF
  - If an authorised Investigator from the reporting site is unavailable, initial reports without causality and expectedness assessment should be submitted to the Sponsor by a healthcare professional within 24 hours of becoming aware of the SAE, but must be followed-up by a medical assessment performed by an authorised Investigator, as soon as possible thereafter.

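### The completers-only rule can bias the primary appetite comparison and leaves out partial data that the protocol itself keeps

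*Combined protocol and SAP*

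**What the plan says.** The opening of Section 7 and Section 7.2 carry the same sentence: "Data from all subjects who completed the study will be included for analysis". The combined document defines no other population: no all-randomised set, no safety set and no rule for missing data. Section 7 points to a trial-specific SAP for detail, but no such definitions appear in the combined document. The sentence is not limited to efficacy. The methods that follow it cover hunger/appetite, hormones, motility, bile acids and the microbiome, and none covers adverse events.

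Two provisions can take a participant out of the study:

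- Section 4.5 names "Safety concerns related to IMP or unacceptable intolerance" among the circumstances for interrupting or stopping treatment.
- Section 5.3 lists "Drugs that can affect gastrointestinal function, motility or sensitivity or gastric acidity" among the prohibited drugs and says: "If these drugs are taken during study medication, IMP medication will be discontinued and the subject will be excluded from the study at that time".

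Two provisions keep the data of those who leave. Section 5.3 adds "Study data up to the time of exclusion will be available", and Section 4.1 says "Trial data and samples collected before withdrawal can be used in the trial".

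The appendix on side effects includes stomach pain and constipation. Section 6.7.2 requires reporting of "All AEs, SAEs and AESIs occurring during Trial treatment or within 30 days after last Trial treatment administration", or up to the last follow-up visit if that comes first. Section 7.1 randomises at most 12 so that about 10 complete.

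**The concern.** In a crossover each participant is their own control, and a completers rule keeps that comparison fair only if leaving is unrelated to how the participant responds. Here the plan contains routes by which it could be related. Someone who gets abdominal symptoms on OCA may stop for intolerance, or may take a drug for those symptoms that Section 5.3 prohibits during treatment. Abdominal symptoms lie close to the primary endpoint of appetite/hunger, so the participants lost could differ from the rest in exactly the quantity being estimated.

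The rule also wastes information. The planned mixed model can use a participant who has only one treatment period. Sections 4.1 and 5.3 retain such data, but Section 7.2 then gives them no role in any analysis. With 12 participants, one or two people matter.

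**Working it through.** **Step 1. Reproduce the planned size.** Inputs from Section 7.1: two-tailed paired t-test, error probability 5%, effect size 1.0, power 80%. Power comes from the noncentral t distribution with n − 1 degrees of freedom and noncentrality 1.0 × √n.

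| Complete pairs | Power at effect size 1.0 |
|---|---|
| 8 | 68.1% |
| 9 | 74.8% |
| 10 | 80.3% |
| 11 | 84.8% |
| 12 | 88.3% |

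Ten is the smallest number that reaches 80%, so the plan's figure is reproduced. The allowance is 12 − 10 = 2, that is 2/12 = 16.7%. A third loss takes power below 80%.

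**Step 2. What selective loss does to the completers analysis.** The documents give no rate or cause of loss, so this step is an illustration. Give each of 12 participants a true OCA-placebo difference D drawn from a normal distribution with mean 0 and SD 1 (no true effect). Give each a tendency to leave u = ρD + √(1 − ρ²)·e, with e an independent standard normal. Remove the participants with the largest u, and apply the paired t-test at two-sided 5% to the rest. Each setting was simulated 200,000 times.

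| Lost of 12 | ρ (assumed) | Absolute bias in mean difference | Two-sided type I error |
|---|---|---|---|
| 1 | 0 | 0 SD | 5.1% |
| 1 | 0.5 | 0.07 SD | 6.1% |
| 1 | 0.9 | 0.13 SD | 8.6% |
| 2 | 0 | 0 SD | 5.1% |
| 2 | 0.5 | 0.14 SD | 7.5% |
| 2 | 0.9 | 0.25 SD | 15.2% |

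The 5.1% at ρ = 0 is the nominal 5% within simulation error. The SD is that of the within-participant difference, the same unit as the plan's effect size, so 0.14 to 0.25 SD is 14% to 25% of the assumed effect of 1.0. The bias has the opposite sign to ρ. If those with the larger positive differences leave, the estimate is pulled down; if those with the more negative differences leave, it is pulled up.

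**Step 3. What could be recovered.** The hunger scores described in the flowchart footnotes are taken during the motility and drinking-test sessions. Those fall before treatment and near the end of each 21-day period (days 17 to 21 and 66 to 70).

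- A participant lost before the first on-treatment session has no post-dose score from these sessions, and no model recovers one.
- A participant lost after that session and before the second has one treated period. The mixed model can use it, with limited information on the within-person contrast.
- With two such participants added to 10 complete pairs, power lies between 80.3% (they add nothing) and at most 88.3% (as good as 12 pairs).

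**Step 4. Set the data provisions side by side.** Sections 4.1 and 5.3 retain data up to withdrawal or exclusion, and Section 7.2 analyses completers only. Section 5.3 ends study participation at the prohibited drug, whereas Section 6.7.2 reports events for up to 30 days after the last dose, subject to the earlier follow-up cut-off. The text does not say how these fit together.

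**The case against.** The strongest objection concerns a larger claim that a reader might infer: that the rule makes OCA look better tolerated than it is, for example 0 of 10 discontinuing instead of 2 of 12. The documents do not support it. Tolerability is not an endpoint, the table in Section 7.2.1 has no adverse-event row, and no discontinuation rate is planned. Events are sought at every contact (Section 6.7), reported without a completion condition (Section 6.7.2), and withdrawal reasons go on the eCRF (Section 8). The 2 is only a dropout allowance, and attributing both losses to OCA would be invention. What remains is narrower: because the completers sentence is not confined to efficacy and no safety set is named, an adverse-event table restricted to completers is not ruled out.

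The routes out can also be overstated. Section 5.3 does not exclude everyone who takes a gut-acting drug; use in the washout only requires at least 2 weeks before the second treatment. Section 4.5 allows interruption as well as discontinuation, so an intolerant participant may still complete, and it provides for continued monitoring after stopping. That participants would self-treat is an assumption. All of this stands, and it makes treatment-related loss possible rather than certain.

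It can also be said that Sections 4.1 and 5.3 only permit and retain data and do not require their analysis. That is fair: this is a gap more than a flat contradiction. Nor will there be much to recover from early dropouts (Step 3). Finally, Section 6.6 treats stomach pain and constipation as not being adverse events for this trial. An all-treated table could therefore still omit them, which is a separate matter.

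**Conclusion.** The point holds for the primary appetite/hunger comparison and, by the same reasoning, for the secondary comparisons. The plan's only analysis population is completers, loss may be related to OCA and to symptoms near the endpoint, and partial data that the protocol keeps are left unused. With the planned allowance of 2 of 12 lost, the illustrative bias runs from 0 to about 0.25 SD and type I error from 5% to about 15%.

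These figures rest on an assumed correlation from 0 to 0.9, on both losses being selected in the same direction, and on a paired t-test in place of the mixed model, which the plan does not specify fully enough to simulate. The documents fix neither the size nor the direction of the bias. They support no conclusion about how tolerable OCA would appear.

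**What to change.** Settle the following before unblinding, so that the choice of population cannot follow the results.

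1. In Sections 7 and 7.2, replace the completers rule. The primary mixed model includes every randomised participant with any post-dose appetite data, analysed by the treatment assigned in each period. Completers become a sensitivity analysis.
2. Report the number, period, treatment and reason for every discontinuation. Using all available data reduces the selection but does not remove it, because a participant lost before the first on-treatment session contributes no post-dose score. Readers need to see who is missing.
3. State that adverse events are summarised for everyone who took at least one tablet, by treatment at onset.
4. Reconcile the Section 5.3 wording, "IMP medication will be discontinued and the subject will be excluded from the study at that time", with the event-reporting window in Section 6.7.2, so that it is clear what is still collected after exclusion.

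The cost is a few sentences, one sensitivity analysis and one table. No extra participants, visits or measurements are needed.

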### 7.2.1 Efficacy Analysis

Endpoint	Statistical Analysis Methods
Primary	mixed models procedure (hunger / appetite)
Secondary	mixed models procedure (whole blood glucose, plasma levels of motilin and ghrelin GLP-1, GLP-2, GIP and insulin), Two-tailed paired t tests or Wilcoxon signed-rank tests (Gastric motility and BA composition), Non-parametric test, multiple testing correction (microbiome data)
Exploratory	Two-tailed paired t tests or Wilcoxon signed-rank tests (Signaling pathway analysis for duodenal biopsies)

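### Paired tests for gastric motility, bile acids and biopsy measures ignore period in this two-period crossover; a period term is cheap protection if a period shift exists

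*Combined protocol and SAP*

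**What the plan says.** The Synopsis describes a placebo-controlled, randomised crossover. Footnote 2 of the Trial Flowchart sets two 21-day treatment periods with a 28-day washout between them.

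For two groups of secondary measures, section 7.2 says: "Gastric motility and BA composition will be compared with Two-tailed paired t tests or Wilcoxon signed-rank tests, depending on data distribution". Section 7 says the same. The table in section 7.2.1 repeats it and applies the same pair of tests to the exploratory analysis of duodenal biopsies.

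Hunger/appetite (primary), the gut hormones and glucose go to a mixed models procedure. It is described only as "taking into account the course of the curves over different time points"; its fixed and random effects are not listed. Section 7 leaves further detail to a trial-specific SAP, and the text available here contains no such detail beyond section 7.

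On the analysis set: "Data from all subjects who completed the study will be included for analysis". Section 7.1 enrols 12 so that "approximately 10 evaluable participants complete the Trial". On allocation, section 7.1 speaks of "6 randomly assigned to Trial treatment and 6 evaluable participants for an estimated total of 12 evaluable participants per treatment group". That sentence is garbled; it hints at 6:6 without saying so. Section 4.3 states neither a ratio nor blocking.

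**The concern.** In a crossover, each participant's difference between obeticholic acid and placebo is also a difference between periods. If responses shift between periods, for instance because participants become used to intubation and endoscopy, the shift enters with one sign in one sequence and the opposite sign in the other. A paired t or signed-rank test treats this as noise, so intervals widen. If the sequences finish with unequal numbers, part of the shift also remains in the treatment estimate, in either direction.

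Nothing else in the plan removes a shift. Section 7.2 reuses the first-period pre-treatment endoscopy and motility data as the second-period baseline. On change scores that single baseline cancels: (OCA − baseline) − (placebo − baseline) = OCA − placebo. Completer-only analysis without a stated allocation scheme leaves sequence balance unprotected.

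**Working it through.** **The plan's own figure.** Section 7.1 uses a two-tailed paired t-test, 5% error, effect size 1.0 and 80% power, and needs 10. With noncentrality 1.0 × √n and n − 1 degrees of freedom, power is 74.8% at n = 9 and 80.3% at n = 10. The stated 10 reproduces. At n = 12 power is 88.3%.

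**Model for the check.** Let d be obeticholic acid minus placebo, scaled so that its SD within a sequence is 1. Let τ be the treatment effect and π the period-2 minus period-1 shift. Then d averages τ − π when obeticholic acid comes first (n_A participants) and τ + π when placebo comes first (n_B), with n = n_A + n_B. The documents give no π, so I assume 0.25, 0.5 and 1.0 SD of the paired difference.

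- Paired t: the mean of all d, n − 1 df. Bias = π(n_B − n_A)/n.
- With a period term: half the sum of the two sequence means of d, SE = √[(1/n_A + 1/n_B)/4], n − 2 df, no bias from π. This equals the treatment coefficient in a participant + treatment + period model.

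**Precision, n = 10 (no effect size needed).** With the term, mean half-width = t × SE × 0.969, where 0.969 is the expected sample SD on 8 df when the true SD is 1:
- 5:5: 2.306 × 0.316 × 0.969 = 0.71
- 6:4: 2.306 × 0.323 × 0.969 = 0.72

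Paired t, by simulation, at π = 0.25, 0.5, 1.0:
- 5:5: 0.72, 0.79, 1.02 (2%, 11%, 44% wider than with the term)
- 6:4: 0.72, 0.78, 1.01

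**Bias of the paired estimate.** 5:5: none. 6:4: 2/10 × π = 0.05, 0.10, 0.20 SD. 7:3: 4/10 × π = 0.10, 0.20, 0.40 SD.

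**Type I error of the paired t (simulation).**
- 5:5: 4.4%, 3.0%, 0.7%
- 6:4: 4.6%, 3.7%, 1.6%
- 7:3: from about 5.4% at π = 0.25 to about 6.3% at π = 1.0

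**Power at τ = 1.0 (illustration only; the protocol assumes this effect for hunger, not for these measures).**
- 5:5: paired t 78%, 72%, 48%, against 79% with the term.
- 6:4, bias against the effect: 74%, 63%, 29%, against 77%.
- 6:4, bias with the effect: 82%, 81%, 69%, against 77%.

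**How likely imbalance is.** From an assumed exact 6:6, two random dropouts can occur in 66 ways. In 36 (55%) one is lost from each sequence, giving 5:5; in 30 (45%) both come from one sequence, giving 6:4. A 7:3 split cannot arise that way; it needs an unequal start, which section 4.3 does not exclude. Averaged over 5:5 and 6:4 and over the direction of the shift, paired t power is 80.2%, 78.2%, 71.8% and 48.8% at π = 0, 0.25, 0.5 and 1.0. With the term it is 0.545 × 79.0 + 0.455 × 77.4 = 78.3%. Break-even is therefore about 0.25 SD.

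**The case against.** The strongest reply is that no period effect is shown. That stands. The large losses need a shift equal to the whole SD of the paired difference, and below about 0.25 SD the term brings no power gain. At 6:4 and 0.25 SD the half-widths are equal. A shift cannot be ruled out in advance either: the flowchart puts the on-treatment visits at days 17 to 21 and 66 to 70, about 49 days apart. That spacing is itself not settled, because footnote 8 dates second-intervention stool sampling to days 28 to 49.

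Second, the separate SAP may specify more. That limits what can be said about the mixed models. A reader might infer that the primary hunger/appetite analysis omits period. The documents do not support that: the terms are unlisted, not shown to exclude it. The paired tests are different, because sections 7, 7.2 and 7.2.1 name them outright.

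Third, a reader might infer that the paired tests generally inflate false positives. They do not at 5:5 or 6:4, where they are conservative if a shift exists. The excess appears at 7:3 and is modest.

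Fourth, these endpoints have no stated power target, so no sizing objective is missed. That stands too, and is why the case rests on interval width and bias rather than on power.

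**Conclusion.** The point holds as a conditional one. The named tests for gastric motility, bile acids and biopsy measures ignore period. If a shift exists, they lose precision: at 5:5 with 10 completers the loss is negligible at 0.25 SD, moderate at 0.5 SD and large at 1.0 SD. With unequal sequences they also give a biased estimate. The sizes rest on assumed shifts, normally distributed differences, 10 completers and splits that the plan neither fixes nor excludes. Priority is low to moderate, since the paired tests apply only to secondary and exploratory measures. The unlisted terms of the mixed models are a minor matter of missing detail.

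**What to change.** In sections 7, 7.2 and 7.2.1, analyse gastric motility, bile acids and biopsy measures from the two on-treatment visits with a linear model: fixed treatment and period, and a participant effect. Keep the planned signed-rank test as a sensitivity analysis where data are skewed. As a minor addition, list the terms of the mixed models for hunger/appetite, hormones and glucose, with period among them. Clarify the allocation sentence in section 7.1 and state the ratio, and any blocking, in section 4.3.

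The cost is wording and one degree of freedom; no extra participants, visits or data are needed. With no shift, power at the illustrative effect of 1.0 SD falls from 80.3% to 79.0% (5:5), 77.4% (6:4) or about 72% (7:3) with 10 completers, and from 88.3% to 87.6% at 6:6. The effect on the mixed models' power was not computed, because their structure is not given. The period term does not address carry-over.
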